The Impact of Microbiota and Associated Blood Tryptophan Metabolites on Pain Perception in Patients Undergoing Lumbar Disc Herniation Surgery

Study Follow-Up Table

Study starting from January 12, 2022, following ethical approval:

1. Ethical approval from the DEU Non-Interventional Ethics Committee is estimated to be obtained in 2022.
2. Commencement of patient data recording following the approval of the Ethics Committee.
3. Regular maintenance of records in the SPSS computer program for the purpose of statistical analysis of the acquired data.
4. Estimated completion of results by November 2022.
5. Conducting statistical analysis after data collection.
6. Evaluation of the correlation between tryptophan metabolites (picolinic acid, 3-Hydroxykynurenone, anthranilic acid, kynurenone, quinolinic acid, kynurenic acid, xanthurenic acid) routinely collected in blood samples after lumbar disc herniation surgeries and Visual Analog Scale (VAS) scores.

Document Date: 30.03.2022

Ethic committee decision dated 31.08.2022, numbered 7131-GO

Study Protocol

1. Introduction

The human body is closely associated with a complex ecosystem known as the microbiota. The microbiota encompasses the total of microorganisms found in various regions of the body, from the digestive system to the skin and respiratory system. These microorganisms can have significant effects on health and disease, and recent research indicates that the gut microbiota, in particular, plays a decisive role in pain perception.[1] [2]

In the past decade, research on the influence of gut microbiota on pain has been increasing.[3] The gut microbiota interacts not only with the digestive system but also with the nervous and immune systems.[4] These interactions may modulate pain mechanisms and contribute to chronic pain. Recent research suggests that gut microorganisms may regulate brain function and behaviour.[5] This has been considered an exciting development in the field of anesthesia, because the effect of intestinal microbiota on pain perception offers a new perspective in the development of anesthesia practices.

Tryptophan can be converted into various metabolites by the gut microbiota, and the effects of these metabolites on pain are being investigated. [6] The effect of the gut microbiota on tryptophan metabolism is an important mechanism in regulating pain perception. [7], [8]

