An important feature of the microbiota is that the signaling molecules it produces through Tryptophan metabolism can affect pain mechanisms. Some bacteria, especially members of the microbiota such as Escherichia Coli, can produce tryptophan.[9] Furthermore, commensal bacterial species that produce AhR ligands play an important role in regulating AhR activity. [10], [11]. The ability of these bacteria to metabolize Tryptophan can lead to the production of the neurotransmitter tryptamine. [12].

Pain is a subjective experience that cannot be directly observed or measured by biological tests. Therefore, the assessment of pain is largely based on the individual's own subjective interpretation. Although its adequacy in pain assessment is questioned, the method used is generally Visual Analogue Scale (VAS).

In this study, we aimed to examine the effect of microbiota and tryptophan metabolites on pain perception in patients undergoing lumbar disc herniation surgery. We evaluated how the gut microbiota affects pain mechanisms by measuring levels of tryptophan metabolites and assessing pain severity in the pre- and postoperative periods.

2. Materials and Methods

In this study, we adhered to the STROBE (Strengthening the Reporting of Observational Studies in Epidemiology) guidelines to ensure the quality and transparency of the reporting of our observational study.

Our study includes 37 lumbar disc herniation (LDH) surgeries performed in Dokuz Eylül University Faculty of Medicine Central Operating Rooms Brain and Nerve Surgery Hall. For the blood samples in which we evaluated tryptophan metabolites; 2 mL of blood was used from the blood samples taken during routine surgery preparation for the patients and from the routine blood samples taken in the postoperative period, and no additional invasive intervention was performed. We elucidated the relationship between tryptophan metabolites (Picolinic Acid, 3-Hydroxykynurenone, Anthranilic Acid, Kynurenone, Quinolinic Acid, Kynurenic Acid, Xanthurenic Acid) and their variations due to microbiota alterations with VAS in acute pain. Preoperative, postoperative, 8th-hour, and 24th-hour blood samples were routinely collected from patients, with 2 ml of sample material used each time. Concurrently, pain information and vital signs were recorded. After the necessary centrifugation processes, the tryptophan metabolites were analyzed by the relevant laboratory team.

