2.1. Data Collection

Blood samples were planned and collected from patients during the preoperative evaluation, at the 8th postoperative hour, and at the 24th postoperative hour, adhering to clinical routines for these procedures. Concurrently with each blood draw, the patient's VAS score, the nature of the pain, and vital signs were recorded. At the end of the surgery, procedures were performed in the recovery unit according to the protocols, and the same data along with vital signs were recorded. Blood samples collected from the patients were centrifuged at 4000 rpm for 10 minutes, after which the serum and plasma portions were transferred to Eppendorf tubes. The blood samples were stored at -80°C for preservation. For the same patients, 24-hour postoperative blood collection was performed, and similar data, including VAS scores, were recorded.

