## Statistical Analysis Plan (SAP)

The Shapiro-Wilk goodness-of-fit test was used to determine whether the distributions of numerical variables conformed to a normal distribution. For numerical variables that followed a normal distribution, descriptive statistics such as mean and standard deviation were provided. For numerical variables that did not follow a normal distribution, descriptive statistics such as median and interquartile range were given. Percentages and frequency tables were provided for categorical variables. To compare the patient and control groups, variables that met the normality assumption were analyzed using the parametric test for the significance of the difference between two means, while those that did not meet the normality assumption were analyzed using the non-parametric Mann-Whitney U test. The assumption of homogeneity of variances was examined with the Levene test statistic. Kruskal-Wallis analysis of variance was used to examine whether there were differences between diagnosis groups in terms of age. The relationship between age and numerical parameters was examined with the Spearman rank correlation coefficient since the age variable did not meet the normality assumption. Whether there were differences in numerical measurements between diagnostic groups was examined with one-way analysis of variance, and when the parametric assumptions of one-way analysis of variance were not met, it was examined with the Kruskal Wallis test. The differences between the groups were examined using the Bonferroni test approach, one of the Post-Hoc tests.

The area under the ROC curve was used to evaluate the performance of the diagnostic test. The Youden index (J), which assumes sensitivity and selectivity, or false positive and false negative rates, as equally important, was used to determine the best cutoff point.

Statistical significance level was accepted as  $p < 0.05$ . Categorical variables are presented as percentages and numbers, and continuous variables are presented as mean (mean), standard deviation (SD) or median, 25th Quarter (Q1) and 75th Quarter (Q3). The suitability of the variables to normal distribution was examined using visual (histogram and probability graphs) and analytical methods (Kolmogorov Smirnov Test). In comparing two independent groups, Mann Whitney U Test was used for those that did not show normal distribution. Spearman correlation analysis was performed to

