evaluate the relationships of continuous variables. In comparing three or more measurements of dependent groups, ANOVA test was used for repeated measurements for data that conformed to normal distribution, and the Friedman test was used for data that did not comply with normal distribution. Wilcoxon test was used for pairwise group comparisons in repeated measurements that were statistically significant. The results were evaluated at a 95% confidence interval, with alpha error set at 0.05. Statistical evaluation was made using the Statistical Package for Social Sciences (SPSS) for Windows 26.0 (IBM SPSS Inc., Chicago, IL) program.

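### Seven VAS–metabolite correlations are each judged at p<0.05 with no primary correlation and no stated adjustment, and the 80% power claim covers only one unadjusted test

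*SAP*

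**What the plan says.** Item 6 of the protocol's Study Follow-Up Table makes the correlation with VAS an aim and lists "tryptophan metabolites (picolinic acid, 3-Hydroxykynurenone, anthranilic acid, kynurenone, quinolinic acid, kynurenic acid, xanthurenic acid", which is seven analytes. Section 2 (Materials and Methods) names the same seven: "We elucidated the relationship between tryptophan metabolites" and VAS in acute pain. It also gives the number of patients: "Our study includes 37 lumbar disc herniation (LDH) surgeries".

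The SAP plans Spearman correlation for relationships between continuous variables. It states the threshold twice: "Statistical significance level was accepted as" p < 0.05, and later "The results were evaluated at a 95% confidence interval, with alpha error set at 0.05". Neither document names a primary metabolite, draw or correlation. Bonferroni appears once in the SAP, for post-hoc differences between groups.

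The SAP's sample size section uses the G*Power point-biserial model with effect size 0.50, alpha 5% and power 80%, and obtains a minimum of 26. It then concludes that the study has adequate power for correlations between VAS and the metabolites, in the plural.

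On timing, section 2.1 records VAS at each draw: "Concurrently with each blood draw, the patient's VAS score". Neither document says which draw or draws enter the correlations.

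**The concern.** The SAP sized the study for these correlations, so they are its main inferential content. Seven tests at 0.05 each do not hold the overall false-positive risk at 0.05. With no primary correlation and no adjustment, one metabolite with p just under 0.05 can be reported as linked to pain, and the plan has no rule for separating it from a result that would survive correction.

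The power statement has the matching weakness. It speaks of the metabolites as a set, while its calculation is for a single test that uses the whole 5%. A reader would credit the study with more support for the set than the calculation gives.

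**Working it through.** **Inputs from the documents.** Seven metabolites (Study Follow-Up Table, item 6); alpha 0.05 (SAP); r = 0.50, power 80%, N = 26, point-biserial model (SAP, sample size section); 37 patients (protocol, section 2). **Assumed.** The pairwise correlation among metabolites, which the documents do not give, is varied from 0 to 0.95. Sidedness is not stated and is inferred in step 1.

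**1. Reproduce the SAP's 26.** In the point-biserial model the test statistic is noncentral t with df = N − 2 and noncentrality δ = √(N·r²/(1 − r²)). At N = 26, δ = √(26 × 0.25/0.75) = 2.94. The two-sided critical value at 0.05 with 24 df is 2.06, so power is 80.6%. N = 25 gives 78.9%. A one-sided test would need only 21. The stated 26 is therefore exactly the answer for one two-sided test with no adjustment.

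**2. Chance of at least one false positive among seven.** If the tests are independent, this is 1 − 0.95⁷ = 1 − 0.698 = 0.302. If the metabolites are correlated, simulated Spearman tests with VAS unrelated to all seven (n = 37) give:

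| Assumed pairwise correlation | At least one p < 0.05 |
|---|---|
| 0 | about 30% |
| 0.5 | about 24–25% |
| 0.8 | about 16% |
| 0.9 | about 12–13% |
| 0.95 | about 10% |

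At the Holm procedure's first step, 0.05/7 = 0.00714, the same kind of simulation gives about 3–5% for correlations from 0 to 0.8.

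**3. Power for one test at r = 0.50.** At N = 37, δ = √(37 × 0.25/0.75) = 3.51.

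| Model | N | alpha 0.05 | alpha 0.05/7 |
|---|---|---|---|
| Point-biserial (the SAP's) | 26 | 80.6% | 51% |
| Point-biserial (the SAP's) | 37 | 93% | 74% |
| Spearman (the planned test), simulated | 37 | about 85–86% | about 62% |

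The Spearman row assumes bivariate normal data, with VAS rounded to the 0–10 scale. On the SAP's model, 80% power at 0.05/7 needs 42 patients (N = 41 gives 79.8%, N = 42 gives 81.1%).

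**The case against.** **The false-positive figure depends on an unknown.** This stands in part. Metabolites of one pathway may well be correlated, and the documents give no values. The 30% is exact only for independent tests and should not be read as the study's own error rate. Even at a pairwise correlation of 0.95, however, the risk is about 10%, twice the stated 0.05.

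**Enrolment passed the planned minimum.** This is true. With 37 patients, one unadjusted test at r = 0.50 has about 93% power on the SAP's model. A reader might infer that the study is underpowered outright, and the documents do not support that. What they show is that the 80% was calculated for one test, and that 37 patients give less than 80% at 0.05/7.

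**The problem may look much larger.** A reader might multiply seven metabolites by the draws and conclude that 21 or 28 tests carry a 66% or 76% risk (1 − 0.95²¹ or 1 − 0.95²⁸, independent tests). The documents do not say that each draw is tested, so those figures are only conditional. The number of draws is itself unsettled. Section 2 lists four ("Preoperative, postoperative, 8th-hour, and 24th-hour blood samples were routinely collected from patients"), while section 2.1 gives three ("Blood samples were planned and collected from patients during the preoperative evaluation, at the 8th postoperative hour, and at the 24th postoperative hour") and adds a recovery-unit record that does not mention blood.

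**The SAP does name a correction.** It names Bonferroni, so it would be wrong to say that it ignores multiplicity altogether. That correction is tied to group comparisons and does not reach the correlations.

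**An observational study can leave such results unadjusted.** Reporting all seven with intervals, labelled exploratory, is a legitimate choice. Neither document calls the study exploratory, and the SAP makes a formal power claim. This objection widens the choice of remedy but does not close the gap.

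**Conclusion.** The concern holds for the seven correlations that the documents name. No primary correlation and no adjustment is stated for them. The chance of at least one false positive is about 30% if the tests are independent and lower if the metabolites are correlated, about 10% at an assumed 0.95. It would be higher if several draws were tested, which the documents do not state. The SAP's 80% power is a single-test figure. At r = 0.50 with 37 patients, power at 0.05/7 is 74% on the SAP's model and about 62% for Spearman.

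These results rest on a two-sided test, inferred because only that reproduces 26; on equal pairwise correlations; and on the SAP's own effect size. They do not show that any particular reported association is false. Nor do the documents show that a metabolite or draw was chosen by its result. This should be fixed, and fixing it is cheap.

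**What to change.** Keep the planned Spearman correlations and add to the SAP:

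- Define the family as all VAS–metabolite correlations actually run: seven if one draw is analysed, otherwise seven times the number of draws.
- Report every one with its estimate, confidence interval, raw p-value and Holm-adjusted p-value.
- Base claims of association on the adjusted values, and label results significant only on the raw p-value as exploratory.
- Do not choose a primary metabolite or draw after results have been seen, and state whether results were known when this rule was set. This matters here because the SAP is written in the past tense and already reports that age failed the normality assumption, and protocol section 2.5 says the study was planned retrospectively.
- Reword the sample size section so that the 80% applies to one unadjusted test. Beside it, give the power at 0.05/7 for n = 37 and name the model: 74% point-biserial or about 62% Spearman.

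**Cost.** SAP wording and a short reanalysis, with no new data. The price is power per test. For Spearman at n = 37 and r = 0.50 it falls from about 85–86% to about 62% at Holm's strictest step. At r = 0.30 it falls from about 40% to 16%. The loss is smaller at Holm's later steps. As an illustration, if all seven metabolites were related to VAS at r = 0.50 and correlated 0.5 with each other, average power per test under Holm would be about 74%. The loss is larger if several draws are tested: at r = 0.50, the strictest step gives about 48% for 21 tests and 44% for 28.

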### **Evaluation of Sample Size Calculation for Correlation Analysis between VAS and Tryptophan Metabolite Measurements**

The sample size calculation for assessing the correlation between VAS (Visual Analog Scale) and tryptophan metabolite measurements was conducted using G\*Power software, employing a Point biserial model test. It was determined that a minimum sample size of 26 participants is required to achieve a statistical power of 80% with a significance level (alpha) of 5% and an effect size of 0.50 (1).

This approach ensures that the study is adequately powered to detect meaningful correlations between pain perception (measured by VAS) and the levels of tryptophan metabolites in the blood, contributing to the robustness of the statistical analysis.

